- A. Control group: Access to the HeadUp app and the wearable tracker
- **B.** Intervention groups: On top of the HeadUp app and the wearable tracker participants will receive a financial incentive intervention for the entire duration of the trial with:
 - **B.1** low value incentives, i.e. low £ per point ratio
 - $\circ~$ **B.2** medium value incentives, i.e. medium £ per point ratio
 - **B.3** high value incentives, i.e. high £ per point ratio

A detailed description of the intervention and baselining logic is provided separately by HUL.

The primary outcomes consist of **2 physical activity outcomes** and **4 dietary outcomes**. The primary physical activity outcomes will be (i) moderate and vigorous physical activity (MVPA) in minutes per day and (ii) daily steps measured objectively through a wearable device. The primary dietary outcomes will be daily intake of (i) fruit and vegetables (g/day), (ii) fibre (g/day), (iii) saturated fat (% of food energy intake) and (iv) free sugars (% of food energy intake) measured through 24 hour dietary recalls. Secondary outcomes will be (i) daily energy expenditure as measured by the wearable, (ii) daily energy intake as measured by 24 hour dietary recalls (Intake24 surveys), (iii) a healthy eating score based on consumption of key food groups, macro- and micronutrients, and (iv) self-reported weight.

Exploratory outcomes will include (i) motivation to change PA and dietary intake as well as (ii) potential unintended health consequences (i.e. mental health and sleep duration). The motivational and mental health outcomes will be measured by in-app mini-surveys, whereas sleep duration will be measured by the wearable.

All primary and secondary outcome data will be collected at the baseline (i.e. pre-randomisation), at one month, three months, and at five months after the randomisation. The exploratory outcomes will be collected at the baseline and at five months after the randomisation.

The pre-planned primary analysis will compare the 2 physical activity outcomes and 4 dietary outcomes at five months post-randomisation between the control group and the three pooled financial incentives groups (i.e. being offered any level of financial incentive).

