Baseline period	Day 1 of baseline: users are invited to provide their first recall. Users are informed that the first two recalls they will provide (to be provided on two separate days, including information about weight) will be remunerated with a payment of £5 each in points. The second intake24 is optional; users are encouraged to complete the second one within 3 days. The survey will be prominently displayed on the dashboard of the app when users open it for the full duration of the baseline period.	If a user owns a wearable device, they are encouraged to sync their own device with the app and provide their PA data from the first day of the baseline period. If a user orders a wearable device, they are encouraged to sync it with the app and provide their PA data as soon as they receive the device. Users will be nudged for the full duration of their baseline period to wear the device and periodically sync it with the app. In the analysis, we will use all valid daily PA data provided during the baseline period (valid = device worn for at least 6h)
1 month mark (starting the 5th week after randomisation)	 Day 1: users are invited to provide a recall. Users are informed that the first two recalls they provide in the following two weeks will be remunerated with a payment of £5 each in points. Reminders, feedback and survey prominence are repeated as per the baseline phase. In the analysis, we will use all recalls submitted during the 5th and 6th week after randomisation for the 1m mark. 	In the 5th week after randomisation, users will be nudged to wear the device as long as possible for 7 days and sync the device with the app. In the analysis, we will use all valid daily PA data provided during the 5th week after randomisation for the 1m mark. If there are missing values in that week, we will impute them with valid values (if available) on the same day of the week within 2 adjacent weeks (i.e. weeks 3-7).

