4.2.1 Methods overview

The quantitative IPE aims to:

- 1. Describe the intervention's reach and users' engagement
- 2. Test key mechanisms of action
- 3. Explore potential 'gaming' and data errors

Table 15 below summarises how the user journey stages map onto the planned quantitative IPE analyses.

User journey stage	Intervention step	Quant IPE analysis	Topic covered
Marketing campaign and acquisition	 Downloading app and in-app consent App usage 	Marketing reach, acquisition, and usage analysis	 Reach Engagement Mechanisms of action Implementation and feasibility
Onboarding	 Mandatory details completion Wearable device connection/use 	Engagement with the intervention and mechanisms of action	 Engagement Mechanisms of action Implementation and feasibility
	5. Intake24 completion	N/A ⁷⁴	N/A
	6. Health surveys	Engagement with the intervention and mechanisms of action	 Engagement Mechanisms of action Implementation and feasibility
	7. Randomisation	N/A ⁷⁵	N/A
Interaction with the intervention (continued app	 'New user journey' of app learning/engagement - first 30 days 	Engagement with the intervention and mechanisms of action	EngagementMechanisms of action
usage)	post-randomisation ⁷⁶ 9. Continued app usage across trial period (completing challenges,	Analysis of 'gaming' and data errors	 Implementation and feasibility

Table 15. Stages	s of user journey	and quantitative	IPE analyses
9	, , , , , , , , , , , , , , , , , , , ,		

⁷⁴ This data concerns the impact evaluation only and will be analysed as part of that.

⁷⁵ This data concerns the impact evaluation only and will be analysed as part of that.

⁷⁶ According to the HUL design plan, this includes: (i) Introduction to app features, (daily) mood check-ins and orientation, through email and push notifications; (ii) Prompts to participate in weekly health challenges focused on PA and nutrition habits; (iii) Survey invites, through push notifications and email – which act as part of the user experience as we are able to better tailor health insights and platform experience with this data; (iv) Milestone celebrations, points and rewards (for incentive groups) and NPS / feedback at 30-day mark. *This is specified here for additional context around the user journey; engagement in these activities will be measured by a set of metrics capturing in-app engagement across the intervention period.*

redeeming incentives etc.)		
-------------------------------	--	--

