In line with the impact evaluation, one cross-cutting focus of the quantitative IPE will be understanding the experience and behaviours of the entire participant sample and of key participant subgroups. For subgroup analyses we will use the same population characteristics and cut offs as those specified for the impact evaluation.

The quantitative IPE makes an important distinction between **engagement with** *intervention components* (e.g. selecting and completing challenges, redeeming rewards), and **engagement with** *evaluation components* (e.g. completing Intake24 surveys). The quantitative IPE is focused on the former; the impact evaluation includes a focus on the latter, as part of attrition management.

The quantitative IPE will use a combination of descriptive analyses (summary statistics and data visualisation) and regression analyses.

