4.2.3. Engagement with the intervention and mechanisms of action

As indicated in the ToC, beyond the initial engagement with the intervention (e.g. providing in-app consent), continued engagement with the app is critical to driving behavioural change in PA and diet activity.

This includes successful onboarding during the baseline stage, selecting and completing challenges, logging behaviours, verifying behaviours, and redeeming incentive rewards.

To explore these themes, the quantitative IPE will analyse the metrics summarised in Table 17. All data will be collected via the app or by reward providers and will be obtained from HUL. The analyses outlined in this section will also rely on HUL sharing the metrics described in Table 17 with BIT.

Table 17. Metrics underlying the 'engagement with the intervention and mechanisms of action' analysis

	Data	Number of	Number of	
Metric	source	timepoints	groups	Which groups
% of consenting participants completing their profile before randomisation (in %)	In-app data	1 (total timespan)	1	Total sample
% of consenting participants connecting the wearable device before randomisation (in %)	In-app data	1 (total timespan)	1	Total sample
% of consenting participants that are active during the "new user journey" (defined as app opened at least once every 7 days over the 30 days after randomisation) (in %)	In-app data	1 (total timespan)	5	Total and by study arm
Average daily number of hours the wearable device is worn from consent to week 24 (in N)	In-app data	1 (total timespan)	5	Total and by study arm
Average daily number of hours the wearable device is worn per week from consent to week 24, by week (in N)	In-app data	22 (weekly)	5	Total and by study arm
Average number of PA challenges selected per week from randomisation to week 24 (in N)	In-app data	1 (total timespan)	5	Total and by study arm
Average number of PA challenges successfully completed per week from randomisation to week 24 (in N)	In-app data	1 (total timespan)	5	Total and by study arm
Average number of PA challenges successfully completed per week by difficulty from randomisation to week 24 (in N)	In-app data	1 (total timespan)	5	Total and by study arm for three difficulty levels
Weekly number of PA challenges successfully completed from randomisation to week 24, by week (in N)	In-app data	22 (weekly)	5	Total and by study arm for three metrics

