Average number of diet challenges selected per week from randomisation to week 24 (in N)	In-app data	1 (total timespan)	5	Total and by study arm
Average number of diet challenges successfully completed per week from randomisation to week 24 (in N)	In-app data	1 (total timespan)	5	Total and by study arm
Average number of diet challenges completed per week by difficulty from randomisation to week 24 (in N)	In-app data	1 (total timespan)	15	Total and by study arm for three difficulty levels
Weekly number of diet challenges successfully completed from randomisation to week 24, by week (in N)	In-app data	22 (weekly)	5	Total and by study arm
Total number of times each challenge has been selected	In-app data	1 (total timespan)	1	Total sample
Total number of times each reward has been selected	In-app data	1 (total timespan)	1	Total sample
Cumulative number of points per week earned (verified) from randomisation to week 24 (in N)	In-app data	1 (total timespan)	5	Total and by study arm

Cumulative number of redeemed rewards from randomisation to week 24 (in N)	Reward partners	1 (total timespan)	5	Total and by study arm
Cumulative \pounds value of redeemed rewards from randomisation to week 24 (in \pounds)	Reward partners	1 (total timespan)	5	Total and by study arm
Average number of PA challenges completed successfully per week from randomisation to week 24, by subgroup (in N)	In-app data	1 (total timespan)	80	Total and by study arm. Each respectively by deprivation status (2 groups), ethnicity (5 groups), sex (3 groups), age (2 groups), baseline F&V intake (2 groups), baseline MVPA (2 groups).
Average number of diet challenges completed per week from randomisation to week 24 (in N) by subgroup	In-app data	1 (total timespan)	80	Total and by study arm. Each respectively by deprivation status (2 groups), ethnicity (5 groups), sex (3 groups), age (2 groups), baseline F&V intake (2 groups), baseline MVPA (2 groups).
Average cumulative number of points earned from randomisation to week 24 (in N) by subgroup	In-app data	1 (total timespan)	80	Total and by study arm. Each respectively by deprivation status (2 groups), ethnicity (5 groups), sex (3 groups), age (2 groups), baseline F&V intake (2 groups), baseline MVPA (2 groups).

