Average cumulative value of redeemed rewards from randomisation to week 24 (in £) by subgroup	Reward partners	1 (total timespan)	80	Total and by study arm. Each respectively by deprivation status (2 groups), ethnicity (5 groups), sex (3 groups), age (2 groups), baseline F&V intake (2 groups), baseline MVPA (2 groups).

Summary descriptive statistics (e.g., averages, proportions) will be calculated using data on all metrics in Table 17 to provide an overview of in-app engagement for the entire participant sample (i.e. all participants who sign up to the app and provide in-app consent, regardless of subsequent data completeness), and split by trial arm.

Additionally, for key metrics related to continued app usage, summary statistics will also be visualised on a weekly basis across the intervention period to provide further insights about how users' behaviour changes over time.

As specified in the table above, to uncover potential differences in engagement between different population segments, **subgroup analyses will be conducted for key metrics, namely:**

- Average number of PA challenges completed from randomisation to week 24
- Average number of diet challenges completed from randomisation to week 24
- Average cumulative number of points earned (**both verified and unverified**) from randomisation to week 24
- Average cumulative value of redeemed rewards from randomisation to week 24

The characteristics and cut offs used for these subgroup analyses will be the same as those employed as part of the impact evaluation.

We will also conduct a regression analysis to identify the factors predicting the cumulative number of points earned from randomisation to week 24, which is used to estimate users' success rate at selecting and completing diet and physical activity challenges. The factors explored in the regression will include age, sex, baseline obesity status (BMI \ge 25), ethnicity, deprivation status, disability status, education, brand of wearable, treatment arm (control, low incentives, medium incentives, high incentives), baseline MVPA, and baseline fruit and vegetable intake. The cut offs for each predictor will be defined following the same criteria used in the impact evaluation (unless specified above).

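### The points outcome in equation (5) mixes recall payments and non-validated claims into a measure meant to capture challenge success

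*Protocol*

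**What the plan says.** Section 4.2.3 of the protocol sets up a regression of the "factors predicting the cumulative number of points earned from randomisation to week 24, which is used to estimate" users' success at selecting and completing diet and physical activity challenges. Equation (5) defines the outcome as all points earned, verified and unverified, and names no source of points to be left out. Treatment enters as four categories with control as the reference. The section says its analyses together address how far incentives affect engagement with specific intervention components. Section 4.2 describes itself as the final version of the quantitative process evaluation.

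Other places bear on what a point is:

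- **Executive Summary, trial arms.** The incentive arms are separated by the value of a point: "low value incentives, i.e. low £ per point ratio" at one end and "high value incentives, i.e. high £ per point ratio" at the other.
- **Section 2.6.1.1, Table 9.** At the 1-month mark the first two recalls "will be remunerated with a payment of £5 each in points", with no restriction by arm. The 3- and 5-month marks work in the same way.
- **Section 4.2.1.** After separating engagement with intervention components from engagement with evaluation components such as Intake24, it states: "The quantitative IPE is focused on the former".
- **Section 4.2.1, footnote 76.** It lists "points and rewards (for incentive groups" among the features of the new-user journey.
- **Section 4.2.3, Table 17.** The points row by arm reads "Cumulative number of points per week earned (verified) from randomisation to week 24 (in N"). The text under the table, on the subgroup points metric, says verified and unverified.
- **Section 4.2.4, Table 18.** The percentage of non-validated points, by arm, is a metric of gaming and data errors.

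**The concern.** The outcome stands in for challenge success, but as defined it also rises when a user completes a dietary recall, which is a data-collection task, and when a user makes a claim that is never validated. If either component differs by arm, the arm coefficients in equation (5) pick up that difference and present it as challenge success. The control reference is also unclear, because the protocol does not say consistently whether control users earn challenge points.

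The process evaluation is meant to help explain whatever the impact evaluation finds, including the comparison of incentive levels. Equation (4) models app opening, so equation (5) is the only regression planned on challenge activity. A pattern across arms that came partly from survey pay could mislead readers about how incentive level works.

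**Working it through.** The plan gives no figure for points, so there is nothing to reproduce. The check has three parts.

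**1. Recall pay by arm**

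Inputs: £5 per recall, up to two recalls at each of months 1, 3 and 5 (Table 9), and retention as 1 minus the Table 6 attrition rate. Assumption: every retained user completes both recalls.

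Expected pay per randomised user = £10 × (retention at month 1 + month 3 + month 5).

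| Arm | Retention | Expected recall pay |
|---|---|---|
| High | 0.82 + 0.56 + 0.38 = 1.76 | £17.60 |
| Medium | 0.82 + 0.55 + 0.37 = 1.74 | £17.40 |
| Low | 0.79 + 0.50 + 0.31 = 1.60 | £16.00 |
| Control | 0.74 + 0.40 + 0.22 = 1.36 | £13.60 |

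At one common rate of £ to points, the high arm would have 17.60 / 13.60 = 1.29 times the recall points of control without a single extra challenge completed. With one recall per retained user every figure halves and the ratio stays the same.

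A full completer can receive 3 × 2 × £5 = £30. The mitigation measures allow £10 per recall at months 3 and 5 and up to £10 for syncing at month 5. The protocol does not say that these are paid in points. If they were, the maximum would be £10 + £20 + £30 = £60. Expected pay would be 10 × 0.82 + 20 × 0.56 + 30 × 0.38 = £30.80 in the high arm and 10 × 0.74 + 20 × 0.40 + 30 × 0.22 = £22.00 in control, a ratio of 1.40.

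**2. Conversion to points**

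The protocol gives neither the £ per point ratios nor the rule for turning a £5 payment into points. Suppose each incentive arm converts at its own rate. Recall points, in units of what £1 buys in the low arm, are then expected pay divided by the arm's relative £ per point:

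| Assumed low : medium : high | Low | Medium | High |
|---|---|---|---|
| 1 : 1.25 : 1.5 | 16.0 | 13.9 | 11.7 |
| 1 : 1.5 : 2 | 16.0 | 11.6 | 8.8 |
| 1 : 2 : 3 | 16.0 | 8.7 | 5.9 |
| 1 : 2.5 : 4 | 16.0 | 7.0 | 4.4 |

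Under this rule the low arm gets the most recall points of the three and the high arm the fewest, the opposite of the order in £. The two rules push the arm comparison in opposite directions, and under neither is it neutral. Points per challenge are not given, so recall points as a share of all points cannot be computed.

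**3. The passages side by side**

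- *Verified or not.* The same non-validated points count towards success in equation (5), are left out of the Table 17 points row, and measure possible gaming or error in Table 18.
- *Control.* Footnote 76 can be read as giving points to the incentive groups. Section 2.5.1 says control users are not rewarded with incentives. Yet Table 9 pays recalls in points without naming an arm, and Tables 17 and 18 report points in total and by study arm. If control earns no challenge points, its value in equation (5) is recall pay alone, and each arm coefficient is partly built in.

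**The case against.** The strongest reply is that nothing in the protocol says recall payments enter the outcome. Section 4.2.3 ties the outcome to challenges, and section 4.2.1 puts Intake24 completion outside the focus of the quantitative process evaluation. Read together, they may intend to leave recall points out, and the delivery partner's design plan, which is not shown, may settle it. This stands as a point about intent. It does not change the definition in equation (5), which has no exclusion.

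Several stronger readings are tempting, and the documents do not support them:

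- *That a different £ value per point is itself a flaw.* If a challenge earns the same points in every arm, points are the neutral unit and £ would be the distorted one. The difference matters only through payments fixed in £.
- *That the comparison is shown to lean towards the low arm.* The reversed order covers recall points only and rests on assumed ratios and own-arm conversion.
- *That points exist only in the incentive arms.* Footnote 76 does not say so. Its bracket may apply to rewards alone, and the footnote is offered as context.
- *That unverified points are gaming.* Section 4.2.4 covers data errors as well. Counting both kinds looks deliberate, since the protocol sets that phrase in bold. If control users have less reason to verify, a verified-only outcome could bias the contrast too.
- *That challenge success is measured only in points.* Table 17 reports challenges selected and completed, by arm, though only descriptively.

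Arm is also just one of eleven factors in the regression, and the section's questions are answered by all its analyses together.

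**Conclusion.** The point holds for the outcome of equation (5) and for the subgroup points metric. As defined, the outcome mixes challenge success with recall completion and with non-validated claims, and the protocol is inconsistent on whether control accrues challenge points. Expected recall pay runs from £13.60 per randomised user in control to £17.60 in the high arm. This assumes Table 6 retention and two recalls per retained user. The direction of the effect on points depends on a conversion rule that the protocol does not give, and the size relative to challenge points is unknown. The documents therefore show an outcome that does not isolate its stated construct, but not a bias of known direction or size. The issue is confined to the process evaluation. No primary, secondary or exploratory impact outcome changes.

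**What to change.** Make the equation (5) outcome the number of physical activity and diet challenges successfully completed from randomisation to week 24. Table 17 already collects this in every arm ("Average number of PA challenges successfully completed per week from randomisation to week 24 (in N") and the matching diet row), in a unit that depends on neither £ per point nor survey pay. State whether a completion must be validated to count.

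If points are kept:

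- exclude recall, sync and survey payments explicitly;
- report verified points and all points side by side;
- make the contrast with control only if control accrues challenge points, after reconciling footnote 76 with Table 9;
- use the same definition for the subgroup points metric.

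Challenge counts need only a wording change and no new data. The price is that counts do not weight challenges by difficulty, but Table 17 reports completion by difficulty separately. Keeping points also requires the delivery partner to supply points by source.

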2.2.4 Randomisation

Randomisation will be conducted at the household level. This approach has two advantages over individual-level randomisation: (i) avoids the risk of contamination within the same household (but opens up the possibility of additive effects of multiple household members being in treatment together); (ii) reduces the risk that we alienate and / or confuse users in the control group whenever they cohabit with someone assigned to a treatment arm.

Users will enter randomisation only if/when they have completed the baseline phase. This implies that the day of randomisation is different across users even within the same households: it always happens at the end of their baseline phase (if successful), but the exact calendar day depends on when they have downloaded the app, when they have completed the onboarding, and how long it took them to complete the baseline phase (see Figure 1 for an example from a user's perspective).

The randomisation algorithm developed by HUL would then:

1. Check if another user from the same household has already been randomised

¹⁴ We consider the attrition too high if the number of users not providing their data is 10% smaller than expected at the start of the 1 month mark (see Table 6 for the expected attrition at different trial stages).

¹⁵ Results for the 5m mark will still be reported; however, we will rely on results from the 3m mark to provide an assessment of the impact of offering financial incentives.

based on their full addresses (including postcode).

- 2. If YES, the algorithm assigns this user to the same trial arm
- 3. If NO, the algorithm generates a random number from 1-100 (inclusive) for the user.
- 4. Based on the rule described in Figure 2, users are assigned to one of the 4 trial arms. Note that the control arm will be larger than the other arms. This is because at the analysis stage (5m mark), we aim at having 3 users in the control group for each user in the treatment arms. However, we expect attrition to differ across control and treatment groups, as shown in Table 6 in Section 2.4.2.4.. Based on these attrition estimates, at randomisation 12% of users will be assigned to the high incentive arm, 12% to the medium incentive arm, 15% to the low incentive arm, 61% to the control arm.

BIT's in-house IT expert will quality assure the code of the randomisation algorithm developed by HUL before the trial launch.

Figure 1. Onboarding and baseline phase from a user's point of view¹⁶.

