2.5 Assignment of interventions

2.5.1 Allocation

To collect comparable baseline data between trial arms, all participants will be able to order a free wearable device if they do not own one, install the pilot app, and initially have access to only the control group version of the app. After baseline data is collected, users will be randomly assigned to one of the four trial arms. Those in the intervention arms would gain access to the incentives and other app features; those in the control arm would have access to the app features but not be rewarded with incentives. All individuals in the same household will be allocated to the same trial arm.⁴⁸

At the analysis stage (end of the trial), we aim at having 3 users in the control group for each user in the treatment arms. However, we expect attrition to differ across control and treatment groups, as shown in Table 6.

⁴⁸ Please note that this does not mean that we are aiming at recruiting a minimum number of households, or that some households will be excluded from the trial, and it won't be a requirement that all household members sign up. This simply means that whenever more than one user belonging to the same household sign up, they will all be allocated to the same trial arm.

Based on these attrition estimates, Table 8 shows the optimal allocation of users to trial arms at randomisation.

Group	E	stimates
	N at the end of the baseline period (at randomisation)	Allocation ratio
1. High incentive	~1,900	12%
2. Medium incentive	~1,950	12%
3. Low incentive	~2,250	15%
4. Control group	~9,400	61%

Table 8. Optimal allocation of users to trial arms at randomisation

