Estimated coefficients and statistical testing for the above predictors will provide robust insights into whether overall engagement with incentives differs by any demographics and baseline PA and diet behaviours. The general equation for estimating the model is similar to that of the impact evaluation:

(5)
$$y_{ij} = \alpha + \beta Treatment_j + \gamma_X X_{ij} + u_{ij}$$

 $u_{ij} \sim N(0, \sigma_u^2)$ for all i, j

where

- y_{ij} is the cumulative number of points earned (**both verified and unverified**) from randomisation to week 24 for participant *i* within household *j*;
- *Treatment* is a categorical variable for treatment group (the categories are control group, low incentives, medium incentives and high incentives, with the control group being the reference category);
- *X_{ij}* are individual level (including age, sex, ethnicity, education, disability status, baseline obesity status, baseline fruit and vegetable intake, baseline

MVPA, and brand of wearable) and family level covariates (e.g. deprivation status) - we will take missing values for these covariates as separate categories rather than imputing;

• u_{ij} is an idiosyncratic error term, which is assumed to follow a Normal distribution (denoted as *N*) of zero mean and a variance of σ_u^2 .

We will use a compound symmetry covariance structure (as is implied by the random intercepts). Linear regression will be used for continuous outcomes, and logistic regression will be used for binary outcomes.

Taken together this analysis section will help to answer following questions:

- Overall, to what extent does the intervention engage participants?
- What characteristics predict participants' engagement with the interventions?
- In what ways did users engage with specific intervention components after signing up?
- To what extent do incentives affect engagement with specific intervention components?

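### Equation (5) pools the unincentivised control arm (about 61% of randomised users) with the incentive arms and has no arm-by-predictor term, so its predictor coefficients do not measure demographic differences in engagement with incentives

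*Protocol*

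**What the plan says.** Equation (5) in protocol section 4.2.3 regresses each participant's cumulative points (verified and unverified, from randomisation to week 24) on arm and a set of predictors. The outcome is a measure "which is used to estimate users' success rate at selecting and completing diet and physical activity challenges". The predictors are age, sex, baseline obesity status, ethnicity, deprivation, disability, education and wearable brand, together with "treatment arm (control, low incentives, medium incentives, high incentives), baseline MVPA, and baseline fruit and vegetable intake". Arm is categorical with control as the reference. The equation has no product of arm with any predictor.

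The text then states what the predictor coefficients are for: to show "whether overall engagement with incentives differs by any demographics and baseline PA and diet behaviours". The same section lists a second question, how far incentives affect engagement, which needs the control arm.

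On who is offered incentives, section 2.5.1 says "those in the control arm would have access to the app features but not be rewarded with incentives". Section 2.2.4 allocates 12% to the high incentive arm, "12% to the medium incentive arm, 15% to the low incentive arm, 61% to the control arm". Footnote 76 in section 4.2.1, describing the first 30 days after randomisation, lists "Milestone celebrations, points and rewards (for incentive groups".

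**The concern.** Arm indicators let the mean number of points differ between arms. They do not let the association of points with, say, deprivation differ between arms. With one slope per predictor, the model averages the association among people who are offered incentives with that among people who are not, and the second group is the larger. A coefficient of that kind answers a question about all app users. It does not answer the question the text sets, which is who engages with the incentives.

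The process evaluation is meant to attend to deprived communities and to inform decisions about scaling up. Equation (5) is the only adjusted and tested analysis of points. If the association is weaker in control, a real gap between groups in the incentive arms is reported too small. If it is stronger in control, the gap is overstated. The *Total* column of Table 17 for points and redeemed rewards, including its subgroup rows, carries the same mixture.

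**Working it through.** **Inputs**
- Expected numbers at randomisation (section 2.5.1, Table 8): high 1,900; medium 1,950; low 2,250; control 9,400.
- Model form (section 4.2.3, equation 5): arm and predictors as main effects, all arms together.
- rho, the control slope divided by the (average) incentive-arm slope: not given. Range shown.

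**Step 1: reproduce the allocation.** The total is 1,900 + 1,950 + 2,250 + 9,400 = 15,500. Control is 9,400 / 15,500 = 60.6%, which rounds to the stated 61%. The incentive arms are 6,100 / 15,500 = 39.4%, which rounds to 39%.

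**Step 2: what the common slope estimates.** In least squares with arm indicators, the common slope is the average of the arm-specific slopes, weighted by arm size times the within-arm variance of the predictor. Randomisation makes that variance about equal across arms, so the weights are the arm shares:

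pooled slope / incentive-arm slope = 0.39 + 0.61 × rho

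| rho | formula | simulated (n = 15,500, 200 replicates) |
|---|---|---|
| 0 | 39% | 39.3% |
| 0.25 | 54% | 55.1% |
| 0.5 | 70% | 70.8% |
| 0.75 | 85% | not run |
| 1 | 100% | 100.2% |

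As an illustration, a 100-point gap in the incentive arms would be reported as about 39, 70 or 100 points at rho = 0, 0.5 or 1. Above rho = 1 the coefficient is inflated (115% at 1.25). With a slope of opposite sign in control it falls below 39%.

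**Step 3: can rho be read from the protocol?** It cannot.
- Footnote 76 ties points and rewards to the incentive groups. If control users earn no challenge points, rho is near 0.
- Table 9 (section 2.6.1.1) pays dietary recalls in points with no arm restriction. Control users may therefore hold points, but these would record survey completion. Section 4.2.1 classes that as engagement with the evaluation and says the quantitative process evaluation is not focused on it.
- Tables 17 and 18 tabulate points in total and by study arm, and section 6 describes the control experience as the same apart from the financial incentives. If control users earn challenge points, rho could be well above 0.

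**Step 4: detection.** Let s be the incentive-arm SD and r the control SD divided by s. For a predictor split 50/50:
- SE, incentive arms only: 2s / √6,100
- SE, pooled: 2s × √(0.394 + 0.606 r²) / √15,500

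Take a gap detectable with 80% power (z = 2.80) in the 6,100 incentive users.
- rho = 0, r = 0 (all control points zero): pooled z = 2.80, power 80%. Only the estimate shrinks. The simulated mean t-statistic was 3.90 with and without control.
- rho = 0, r = 1: pooled z = 0.394 × 2.80 × √(15,500 / 6,100) = 1.76, power 42%.
- rho = 1, r = 1: pooled z = 2.80 × √(15,500 / 6,100) = 4.46, power about 99%.
- Break-even at r = 1: 0.394 + 0.606 × rho = √(6,100 / 15,500) = 0.627, so rho is about 0.385. Above that, pooling has more power than the incentive-arm fit.

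**The case against.** The strongest reply is that control belongs in the model. The section asks how far incentives change engagement, and the outcome is described as a proxy for success at challenges, which control users can also take up in a near-identical app. For that broader question an all-arm average is legitimate, and where slopes are similar across arms pooling is more precise. This stands, and it rules out simply dropping control from equation (5).

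A second reply is that Table 17 already plans points and redeemed-reward value by subgroup, in total and by study arm: 16 subgroup levels (2 + 5 + 3 + 2 + 2 + 2) times 5 columns gives its 80 groups. Only the baseline fruit-and-vegetable and MVPA splits depend on contract (Appendix D3). A deprivation gap in each incentive arm will therefore be visible without dilution. This limits the harm. Those figures are unadjusted and untested, however, and do not correct the reading of the regression.

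A reader might go further and infer that every demographic difference is cut to 39% of its size, or that real gaps will be missed. The documents support neither. The 39% needs control points to be unrelated to the predictor, which the protocol does not establish. Loss of power needs control points that vary but bear little relation to the predictors. Nor can it be said that control users could earn no points at all, given the recall payments in Table 9.

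**Conclusion.** The point holds as a mismatch between model and stated purpose. Each predictor coefficient in equation (5) is an arm-weighted average, and is not the demographic difference in engagement with incentives that the text says it is. Its size relative to the incentive-arm value is 0.39 + 0.61 × rho, and rho is unknown from the protocol.

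This rests on the planned allocation being realised, on similar predictor distributions across arms (which randomisation gives), and on all randomised users being analysed. If only users retained at five months were analysed, with the planned 2,100 of 4,200 in control, the factor would be 0.5 + 0.5 × rho.

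The importance is minor to moderate. It concerns one process-evaluation regression and the *Total* cells of one table. The primary and secondary impact analyses do not depend on it.

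**What to change.** 1. Keep the all-arm equation (5) for the effect of arm and for overall challenge engagement, and describe its predictor coefficients as averages across all users.
2. For the question on engagement with incentives, add an any-incentive-by-predictor term for each predictor, or a supplementary fit in the three incentive arms with low, medium and high indicators. Report the incentive-arm coefficients.
3. In Table 17, add an *any incentive (pooled)* column beside *Total* for the points and redeemed-reward rows and their subgroup rows.
4. State whether control users accrue points, and from what (challenges, recalls or both), so that readers can judge how far the two sets of coefficients should differ.

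The cost is some wording, one extra model and one extra column, with no new data. The statistical price is wider intervals for the incentive-arm coefficients, which rest on about 6,100 users instead of 15,500, if the slopes are in fact similar across arms. Keeping the all-arm model alongside preserves that precision for the broader question.
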